3.6. Safety Endpoints

Safety assessments will include treatment-emergent adverse events and serious adverse events, including deaths, vital signs (temperature, systolic and diastolic blood pressure, heart rate, respiratory rate, oxygen saturation), clinical laboratory evaluations (serum chemistry, hematology, coagulation, urinalysis), 12-lead ECGs, physical examination including specific neurology assessments.

3.7. Adverse Events

An adverse event is defined as any untoward medical occurrence in a clinical investigation patient administered a pharmaceutical product, which does not necessarily have a causal relationship with this treatment. An adverse event can therefore be any unfavorable and/or unintended sign (including an abnormal laboratory finding), symptom, or disease temporally associated with the use of an IMP, whether or not related to the IMP. Any adverse event that started on or after the administration of study drug will be considered a treatment emergent adverse event (TEAE). AEs will be captured from the time of initial dosing through the Follow-Up Visit. Events that occur after Day 42 (maximum duration of treatment with fosmanogepix) but prior to and including the Follow-Up visit will be considered treatment

emergent. All AEs will be coded to system organ class (SOC) and preferred term (PT) using the MedDRA.

3.8. Clinical Laboratory Evaluations

Screening laboratory assessments to determine eligibility will be performed at the local laboratory and may have been collected as SOC within the previous 24 hours. Laboratory assessments collected after Screening will be sent to the central laboratory for analysis.

Clinical laboratory assessments (serum chemistry, hematology [including CBC with differential], coagulation [including PT/INR], and urinalysis) will occur at Screening; predose on Days 1 (Baseline), 7, 14, 28, and 42; at EOST; and at the E/T Visit (if applicable).

A urine or serum pregnancy test will be performed at Screening; on Days 1 (Baseline) (if the Screening Visit occurred ³96 hours prior to Day 1 [Baseline]), 28, and 42; at EOST; at the Follow-Up Visit; and at the E/T Visit (if applicable) for all women of childbearing potential.

3.9. Vital Signs

Vital signs will include temperature, blood pressure, heart rate, respiratory rate, and oxygen saturation and will be collected at Screening; predose on Days 1 (Baseline), 7, 14, 21, 28, 35, and 42; at EOST; at the Follow-Up Visit; and at the E/T Visit (if applicable).

3.10. Electrocardiograms

A 12 lead ECG will be obtained in triplicate at Screening, Days 3, 7, 14 and 42, EOST, and the E/T Visit (if applicable).

3.11. Physical Examinations

Complete physical examinations were conducted at Screening, Day 42, EOST, and the E/T Visit (if applicable). A complete physical examination will include an assessment of general appearance, skin, eyes, heart, chest, abdomen, and a neurological examination. Components of the neurological examination include cranial nerve, sensory, and motor examination; reflex and gait testing; and coordination assessment. Height will be measured at Screening and weight will be measured at Screening; on Days 1 (Baseline), 7, 14, 21, 28, 35, and 42; at EOST; at the Follow-Up Visit; and at the E/T Visit (if applicable).

A neurological examination (all patients) and a symptom-directed physical examination will be conducted as clinically indicated (ie, new signs or symptoms and follow-up on earlier findings) on Days 1 (Baseline), 7, 14, 21, 28, 35, and at the Follow-Up Visit.

[figure not shown]
4. ANALYSIS SETS (POPULATIONS FOR ANALYSIS)

Data for all participants will be assessed to determine if participants meet the criteria for inclusion in each analysis population prior to unblinding and releasing the database and classifications will be documented per standard operating procedures.

Population	Description	Applicable Analysis
ITT	All participant entered to the study	
Modified Intent- to-Treat (mITT)	The modified Intent-to-Treat (mITT) Population will include all patients in the ITT Population who satisfy the following criteria:	The mITT Population will be the primary population used for the efficacy analyses
	Receive at least 1 dose of study drug.	
	Cohort a: have a diagnosis of proven or probable IMI confirmed by the DRC.	
compliance	The Per-Protocol Population will include all patients in the mITT Population who satisfy the following criteria: • Meet the protocol's key inclusion criteria and exclusion criteria. • Receive at least 80% of the intended doses; and • Have no major protocol violations, ie, not received any prohibited concomitant medications per the protocol that would impact the efficacy of study drug.	Per protocol analyses will not be performed due to the small size of the study and due to design of study (eg, open label). This has been documented in the study log.
Safety	All participants who receive at least 1 dose of study intervention.	For all safety endpoints
PK population	The PK Population will include all patients who receive any amount of study drug and have evaluable PK data.	For PK parameters

5. GENERAL METHODOLOGY AND CONVENTIONS

5.1. General Considerations

5.2. Hypotheses and Decision Rules

The primary hypothesis for Cohort A is that the mortality rate at Day 42 is <45% based on 1-sided exact binomial test at the alpha = 0.1 level of significance.

The hypothesis will be as follows:

 H_0 : π ≥45%

H_a: $\pi < 45\%$

where π is the all-cause mortality through Day 42. 1-sided 90% confidence interval (CI) or two-sided 80% CIs will be provided. It can be concluded that the all-cause mortality at Day 42 is less than 45% (based on historical control data) if the upper limit of the CI is lower than 45%.

5.3. General Methods

5.3.1. Analysis Day

Analysis day will be calculated from the date of first dose of study drug. The day of the first dose of study drug will be Day 1, and the day immediately before Day 1 will be Day -1. There will be no Day 0.

5.3.2. Analysis Visits

Scheduled visits will be assigned to analysis visits as recorded on the CRF.

5.3.3. Definition of Baseline

For microbiological data, baseline pathogen(s) are *Aspergillus* spp. or rare molds (eg, *Scedosporium* spp., *Fusarium* spp., *Lomentospora* spp., and Mucorales fungi, etc.) isolated from the last positive fungal culture sample collected prior to the first dose of study drug.

For all efficacy and safety endpoints, baseline is defined as the last measurement or assessment prior to first dose of study drug.

5.3.4. Summary Statistics

Summary statistics will be presented for Cohort A only. For continuous variables, the number of observations (n), mean, standard deviation, median, minimum, and maximum will be provided. For categorical variables, the frequency and percentage in each category will be displayed.

5.3.5. Analyses for Binary Endpoints

For all binary endpoints, proportion of participants and 95% CI will be presented.

5.3.6. Analyses for Continuous Endpoints

For continuous endpoints, mean (SD), median, max, min will be presented.

5.3.7. Analyses for Categorical Endpoints

For categorical endpoints, number and percentage will be presented with the associated sample size.

5.4. Methods to Manage Missing Data

Patients who dropped out or had missing outcome data will be included in the denominator for efficacy analyses. If any patient has missing global response, clinical response, radiological response, or mycological response from the DRC or Investigator at EOST, it will be presented as missing in the summary.

In cases of missing or incomplete dates (eg, Adverse event [AE] and concomitant medications), the missing component(s) will be assumed as the most conservative value possible. For example, AEs with missing start dates, but with stop dates either overlapping into the treatment period or missing, will be counted as treatment-emergent, taking the worst-case approach. When partial dates are present in the data, both a partial start date and/or a partial stop date will be evaluated to determine whether it can be conclusively established that the AE started prior to the start of study drug or ended prior to the start of study drug. If the above cannot be conclusively established based on the partial and/or present dates, then the AE will be considered as treatment emergent. Actual data values as they appear in the original electronic Case Report Form (eCRF) will be presented in the data listings.

Missing values for other variables will not be imputed and only observed values will be used in data analyses and summaries.

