# 6.3.9 Day 42 (± Days)

If EOST procedures are performed after Day 39, Day 42 procedures will not be required. The following procedures will be performed on Day 42 ( $\pm 2$  days):

- Administer 600 mg APX001 by IV infusion over 3 hours QD or 800 mg APX001 PO QD.
- Record Investigator assessment of global response.
- Assess survival status.
- Perform urine or serum pregnancy test on women of childbearing potential only.
- Perform a complete physical examination including assessment of general appearance, skin, eyes, heart, chest, abdomen, and a neurological examination and measure weight.

- Assess clinical signs and symptoms.
- Record vital signs, including temperature, blood pressure, heart rate, respiratory rate, and oxygen saturation.
- Perform 12-lead ECG in triplicate.
- Perform clinical laboratory assessments (serum chemistry, hematology [including CBC with differential], coagulation [including PT/INR], and urinalysis).
- Perform CT scan if clinically indicated.
- Collect serum samples for analysis of CCI and C.
- Collect samples for fungal cultures (eg, from BAL fluid, sputum, bronchial brush, sinus aspirate, tracheal aspirate) as clinically indicated.
- Collect BAL samples per SOC for culture and CCI testing as clinically indicated.
- Collect plasma PK samples predose for IV dosing or at any time in clinic for PO dosing.
- Record concomitant medications.
- Assess adverse events.
- Review accountability for all returned study drug.

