# 7 EFFICACY ASSESSMENTS

#### 7.1 Primary Efficacy Endpoint

The primary efficacy parameter is the following:

• All-cause mortality through Day 42.

**Note:** All-cause mortality will represent the percentage of patients who die after the first dose of study drug through Day 42 from any cause.

Every attempt must be made to record survival status at Day 42 or anytime thereafter for all dosed patients, regardless of their status of treatment, as long as the patient has not withdrawn consent from participation in the study. An in-person assessment is preferred; however, this assessment may also be performed via a telephone call if an in-person visit is not possible.

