2.4. Sample Size Determination

Approximately 50 patients will be dosed in this open-label, parallel-group study, and will be enrolled in one of 2 cohorts, as follows:

Cohort A (~40 participants):

Patients with proven or probable IMI are eligible for inclusion in the mITT Population, which is the primary efficacy population (DRC confirmation required of proven or probable IMI).

The sample size calculation is based on the mITT Population from the first dose of fosmanogepix through EOST (up to 6 weeks) for the all-cause mortality primary endpoint. A total of 24 patients in the mITT Population are needed, providing >90% power to detect the difference at a 1-sided significance level of 0.1, assuming an all-cause mortality of 20% for fosmanogepix and 45% for adjusted amphotericin B-treated all-cause mortality from the historical control. Assuming 60% of dosed patients will be eligible to be included in the mITT Population, dosing of approximately 40 patients allows for statistical testing of proof-of-concept for an estimate of 24 patients in the mITT Population.

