3. ENDPOINTS AND BASELINE VARIABLES: DEFINITIONS AND CONVENTIONS

3.1. Primary Efficacy Endpoint(s)

The primary efficacy parameter is all-cause mortality through Day 42.

Note: All-cause mortality will represent the percentage of patients who die after the first dose of study drug through Day 42 from any cause.

Every attempt must be made to record survival status at Day 42 or any time thereafter for all dosed patients, regardless of their status of treatment, as long as the patient has not withdrawn consent from participation in the study. An in-person assessment is preferred; however, this assessment may also be performed via a telephone call if an in-person visit is not possible.

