6.2. Main Analysis

All-cause mortality through Day 42 is calculated as the percentage of patients who die after the first dose of study drug through Day 42 from any cause using the mITT population.

For Cohort A only, the 1-sided exact binomial test at the alpha = 0.1 level of significance will be used to test the hypothesis as below:

H0: π ≥45%

Ha: $\pi < 45\%$

where π is the all-cause mortality through Day 42. 1-sided 90% confidence interval (CI) or two-sided 80% CIs will be provided. It can be concluded that the all-cause mortality at Day 42 is less than 45% (based on historical control data) if the upper limit of the CI is lower than 45%.

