Appendix 1. Summary of Efficacy Analyses

Endpoint	Analysis Type	Population	Data Inclusion and Rules for Handling Intercurrent Events and Missing Data	Analysis Model
Primary endpoint: Mortality rate at Day 42.	Primary	mITT	All observed data.	Cohort A: One-sided exact binomial test at the alpha = 0.1 level of significance:
Secondary Endpoint: Global response at EOST	Secondary	mITT	All observed data	Cohort A: Two-sided 80% exact binomial CI
Clinical responses	Other	mITT	All observed data	Cohort A: Two-sided 80% exact binomial CI
Radiological response	Other	mITT	All observed data	Cohort A: Two-sided 80% exact binomial CI
Mycological response	Other	mITT	All observed data	Cohort A: Two-sided 80% exact binomial CI
CCI				

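### Under SAP 5.4 and 6.2 a patient with unknown Day 42 survival counts as alive, which favours success in the primary mortality test

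*SAP*

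**What the plan says.** SAP 5.4 sets the denominator for all efficacy analyses: "Patients who dropped out or had missing outcome data will be included in the denominator for efficacy analyses". SAP 6.2 sets the numerator: "All-cause mortality through Day 42 is calculated as the percentage of patients who die after the first dose of study drug through Day 42", in the mITT population. SAP 3.1 defines the endpoint in the same way.

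Nothing else assigns an outcome to a patient of unknown survival. The missing category in SAP 5.4 covers global, clinical, radiological and mycological response only. SAP Appendix 1, in its column on missing data, enters "All observed data" for the primary endpoint.

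Protocol 7.1 tries to keep unknowns few: "Every attempt must be made to record survival status at Day 42 or anytime thereafter for all dosed patients", by telephone if need be. The exception is withdrawn consent; the instruction applies "as long as the patient has not withdrawn consent from participation in the study".

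**The concern.** A patient who is in the denominator and is not a recorded death is, arithmetically, a survivor. The SAP does not state this; it follows from applying the two sections as written.

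Keeping missing patients in the denominator is a cautious rule for response, because it lowers the success rate. For mortality the direction reverses, because success means showing a rate below 45%. For missing dates, SAP 5.4 itself chooses the most conservative value. For the primary endpoint, its denominator rule does the opposite.

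This is the trial's only hypothesis test, planned on about 24 patients, so near the cut-off one patient of unknown status can decide whether proof of concept is declared.

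**Working it through.** **Inputs from the documents.** H0: mortality ≥45%, one-sided exact binomial test, alpha 0.1, success if the upper confidence limit is below 45% (SAP 5.2, 6.2). 24 mITT patients, 20% assumed mortality on treatment, power above 90%, 60% of about 40 dosed patients in the mITT (SAP 2.4).

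**Assumptions.** The documents give no rate of unknown survival, so u = 0 to 3 unknowns is assumed. Known and unknown patients are given the same true mortality.

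**Step 1: reproduce the plan.** The cut-off c(n) is the largest k with P(X ≤ k | n, 0.45) ≤ 0.10. For n = 24, c = 7.
- Type I error: P(X ≤ 7 | 24, 0.45) = 0.0863.
- Power: P(X ≤ 7 | 24, 0.20) = 0.9108.
- Dosed patients: 24 / 0.60 = 40.

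The stated power above 90% is correct when every outcome is known.

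**Step 2: unknowns scored alive, n = 24.** Deaths can be recorded only among the 24 − u known patients, but the cut-off stays at 7. Type I error = P(X ≤ 7 | 24 − u, 0.45).

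| u | Type I error |
|---|---|
| 0 | 0.0863 |
| 1 | 0.1152 |
| 2 | 0.1518 |
| 3 | 0.1971 |

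**Step 3: dependence on n.** The test is discrete, and 24 is itself only "an estimate" in the sense of SAP 2.4 ("dosing of approximately 40 patients allows for statistical testing of proof-of-concept for an estimate of 24 patients in the mITT Population"). The cut-off is 6 for n = 22 and 23, and 7 for n = 24 to 26. One unknown scored alive gives:

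| n | Type I error, u = 1 |
|---|---|
| 22 | 0.0964 |
| 23 | 0.0705 |
| 24 | 0.1152 |
| 25 | 0.0863 |
| 26 | 0.0639 |

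Averaged over n as Binomial(40, 0.6), an assumption, the type I error is 0.068, 0.092, 0.123 and 0.162 for u = 0, 1, 2 and 3. On average one unknown does not breach 0.10, and two do.

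**Step 4: a case on the cut-off.** 24 patients, 7 known deaths, 1 unknown; one-sided 90% Clopper-Pearson upper limits:

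| Unknown scored as | Data | Exact p | Upper limit | Result |
|---|---|---|---|---|
| Alive | 7/24 | 0.0863 | 44.2% | Success |
| Excluded | 7/23 | 0.1152 | 45.9% | Failure |
| Dead | 8/24 | 0.1730 | 48.4% | Failure |

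Away from the cut-off the scoring may not matter: 5 deaths plus 2 unknowns scored dead is 7/24, still success.

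**Step 5: how often the scoring decides the result at 20% mortality, n = 24.** P(X ≤ 7 | 24 − u, 0.20) − P(X ≤ 7 − u | 24 − u, 0.20) = 0.088, 0.211 and 0.371 for u = 1, 2 and 3. At that mortality success is the right conclusion, so these figures measure sensitivity to the rule and do not count false successes.

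**The case against.** **The scoring is implied, not written.** Appendix 1 could be read as excluding unknowns. At 24 patients, with the cut-off reset to the reduced number, exclusion gives a type I error of 0.051, 0.071 or 0.096 for 1, 2 or 3 unknowns, so there is no breach. But that reading contradicts SAP 5.4, which keeps these patients in the denominator. On neither reading does an unknown count as a death.

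**Unknowns may be rare.** This stands. Survival is assessed at Day 42, at EOST and at the Day 84 call. Deaths are serious adverse events, reportable within 24 hours until the Follow-Up Visit (Protocol 8.2, 8.3). Protocol 4.3 requires contact attempts for patients lost to follow-up. The Follow-Up Visit also shows survival past Day 42 for anyone whose EOST is on Day 17 or later (17 + 28 − 3 = 42). What remains is withdrawn consent and true loss to follow-up. Survival status is also not among the Early Termination Visit procedures in Protocol 6.7.

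**The inflation rests on assumptions.** It fixes the number of unknowns and gives them 45% mortality; an unknown patient who is in fact alive is scored correctly. Crossing 0.10 with a single unknown occurs at n = 24 but not at 22, 23, 25 or 26. These limits stand, but not the direction: each unknown scored alive can only make success easier than scoring that patient dead.

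**Counting unknowns as deaths is one convention among several, and it costs power.** True. It is nevertheless a common cautious choice for a mortality endpoint, and it matches the worst-case approach SAP 5.4 takes elsewhere.

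**Conclusion.** The concern holds. Followed literally, the SAP scores an unknown Day 42 status as a survivor in the trial's only hypothesis test, and that favours success. At 24 patients and 45% mortality in known and unknown patients alike, the type I error rises from 0.086 to 0.115, 0.152 or 0.197 with 1, 2 or 3 unknowns. Averaged over the uncertain mITT size, it takes two unknowns to exceed 0.10. With no unknowns there is no effect, and the documents give no rate from which to judge how many to expect. This should be fixed before the SAP is final; it does not invalidate the design, and the planned sample size and power are correct for complete data.

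**What to change.** For the primary endpoint only, state in SAP 5.4, 6.2 and Appendix 1:

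1. A patient known to be alive at any contact on or after Day 42, including the Day 84 call, is a survivor.
2. A death dated through Day 42 is a death, whenever it is learned.
3. A status still unknown after all contacts counts as a death in the primary test and its confidence interval.

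Report observed-only or Kaplan-Meier mortality as a sensitivity analysis, and replace the Appendix 1 entry for this endpoint with this rule. A minor addition: say whether being alive on Day 40 or 41 suffices, since the SAP's Day 42 window runs from Day 40 to 44 and Protocol 6.3.9 waives the Day 42 visit when EOST falls after Day 39.

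The cost is SAP wording and, only if a status is unknown, a less favourable estimate and a stricter test. At n = 24, with type I error P(X ≤ 7 − u | 24 − u, 0.45) and power P(X ≤ 7 − u | 24 − u, 0.20):

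| Unknowns counted as deaths | Type I error | Power at 20% |
|---|---|---|
| 0 | 0.086 | 0.911 |
| 1 | 0.051 | 0.840 |
| 2 | 0.027 | 0.733 |
| 3 | 0.013 | 0.586 |

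Items 1 and 2 come first because they reduce the number of patients to whom item 3 applies.

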6. ANALYSES AND SUMMARIES

6.1. Primary Endpoint(s)

All-cause mortality through Day 42 will be summarized for Cohort A using descriptive statistics.

6.2. Main Analysis

All-cause mortality through Day 42 is calculated as the percentage of patients who die after the first dose of study drug through Day 42 from any cause using the mITT population.

For Cohort A only, the 1-sided exact binomial test at the alpha = 0.1 level of significance will be used to test the hypothesis as below:

H0: π ≥45%

Ha: $\pi < 45\%$

where π is the all-cause mortality through Day 42. 1-sided 90% confidence interval (CI) or two-sided 80% CIs will be provided. It can be concluded that the all-cause mortality at Day 42 is less than 45% (based on historical control data) if the upper limit of the CI is lower than 45%.

6.3. Secondary Endpoint(s)

Global response at EOST. Global responses will be classified as complete or partial response (categorized as treatment success), stable response, progression of fungal disease, or death (categorized as treatment failure) by the Investigator and adjudicated by the DRC.

Number and percentage of patients in the mITT Populations with global responses at EOST as determined by the DRC will be tabulated for Cohort A. Two-sided 80% exact binomial CIs of the treatment success rate will be presented for Cohort A only.

Global response will also be summarized descriptively as, complete response, partial response, stable response, progression of fungal disease, death at EOST, ET and EOST/ET (LOCF).

6.4. Other Endpoint(s)

6.4.1. Clinical Responses

Clinical responses will be assessed by DRC and by investigator will be classified as complete response, partial response, stable response, and failure. Number and percentage of patients in the mITT Populations with clinical responses at EOST as determined by the DRC will be tabulated for Cohorts A. Two-sided 80% exact binomial CIs of the treatment success (complete and partial response) rate will be presented for Cohort A.

Clinical responses at EOST as determined by the Investigator will be tabulated in the same manner.

